8.4.5. Reporting Procedure to IRB and to the FDA in the United States

The Investigator must report all SAEs to the Sponsor/CRO immediately, within 24 hours (see Section 8.4.1).

In addition to reporting the SAE to Dompé/CRO, the Investigator must also comply with the requirements related to the reporting of SAEs to the IRB which approved the study. As a minimum requirement, the Investigators must promptly report all SUSARs to their IRB.

Reporting of Suspected Unexpected Serious Adverse Reaction

In line with provisions set forth in 21CFR312, the Sponsor shall notify the Investigators and the FDA in an IND safety report of any SUSAR and of potential serious risks, from clinical trials or any other source, as soon as possible, but in no case later than:

- seven calendar days after becoming aware of the information if the event is fatal or life threatening; to be followed by any relevant information within eight days.
- fifteen calendar days after becoming aware of the information if the event is neither fatal nor life threatening.

The Investigators in turn shall notify their IRB: Investigators are required to promptly report "to the IRB all unanticipated problems involving risk to human subjects or others," including AEs that should be considered unanticipated problems (21 CFR 312.66).

The blind should ordinarily be broken for IND safety reports submitted to FDA and all participating investigators. Dompé Global Pharmacovigilance, Safety and Surveillance Department will unblind treatment prior to regulatory submission of a potential SUSAR to FDA and IRB and only cases referred to active treatment will be considered expeditable for regulatory reporting, in line with law requirements. In general, if the blind is broken and the subject was receiving placebo, the event should not be reported in an IND safety report because there is not a reasonable possibility that the drug caused the adverse event.

If the results of an investigation show that an AE not initially determined to be reportable is reclassified as reportable, Dompé Drug Safety Department shall notify such SUSAR in a written safety report as soon as possible, but in no event later than 7/15 calendar days after the determination is made.

Copies of all correspondence relating to reporting of any SAEs to the IRB should be maintained in the Investigator's Files.

Potential serious risks arising from clinical trials or any other source, to be reported to FDA and to the Investigators, include:

- any SUSAR. Dompé must report an adverse event as a suspected adverse reaction only if there is evidence to suggest to the Sponsor a causal relationship between the drug and the adverse event.
- findings from other studies that suggest a significant risk in humans exposed to the drug. Such a finding would result in a safety-related change in the overall conduct of the clinical investigation.
- findings from animal or in vitro testing that suggest a significant risk in humans exposed to the drug
- increased rate of occurrence of serious suspected adverse reactions.

Based on the specific Investigator's site requirements, Dompé Global Pharmacovigilance, Safety and Surveillance Department will submit to IRBs and Investigators periodical safety updates, as per applicable local requirements and regulations.

Dompé Global Pharmacovigilance, Safety and Surveillance Department shall also be responsible to prepare and submit annual safety reports (Development Safety Update Report - DSUR) to FDA and IRBs (Director of Clinical Trial Regulatory Affairs at AHN).

8.5. EXPOSURE TO IMP DURING PREGNANCY

Women of childbearing potential are defined as all women physiologically capable of becoming pregnant. Prior to enrolment in the clinical trial, female patients of childbearing potential and their partners must be advised of the importance of avoiding pregnancy during the entire course of the study treatment and for the 2 months after the study discharge and of the potential risks associated with an unintentional pregnancy. During the trial (treatment period or follow up period), female patients are to be instructed to contact the Investigator immediately if they suspect they might be pregnant. In the same way, male patients who become aware that the partner might be pregnant, are to be instructed to contact the Investigator immediately.

The Investigator must report every pregnancy on a pregnancy report form as soon as possible (within 24 hours of learning of the pregnancy to the Pharmacovigilance Contacts specified in the section "Contact Information", even if no AE has occurred, and follow it to term. If, however, the pregnancy is associated with an SAE (e.g. if the mother is hospitalized for dehydration), in addition to the pregnancy report form, a separate SAE report form must be filed as described in Section 8.6, with the appropriate serious criterion indicated on the SAE report form. Miscarriage, stillbirth and any malformation/disease must be reported as a SAE.

Any pregnancy leads to the immediate withdrawal of the study subject from the trial.

8.6. ADVERSE EVENTS CAUSING TREATMENT DISCONTINUATION

If a patient is withdrawn from the study as a consequence of an AE, this must be recorded and reasoned in the eCRF, and the patient must be followed up until the resolution of the AE or as instructed by the medical expert.

8.7. OVERDOSE

Accidental or intentional overdose, which may or may not result in serious adverse reactions, is to be reported to CRO Pharmacovigilance, Dompé Global Pharmacovigilance, Safety and Surveillance Department and to Dompé Medical Expert, following the same procedure for SAE, within 24 hours from the Investigator's knowledge of its occurrence. This includes reports related to drug intake through different routes (e.g. ingestion) or with suicidal intentions and consequent drug overdose.

An overdose of ladarixin is defined as the administration of 6 or more capsules on any given treatment day.

The Investigator shall provide in the SAE form information about symptoms, corrective treatment and outcome of overdose. The Medical Expert should be contacted to discuss corrective treatment, if necessary.

8.8. EMERGENCY PROCEDURES AND UNMASKING OF STUDY TREATMENT

The treatment allocation for each patient will be provided with a protected system to:

- the Principal Investigator and study physicians for emergency procedures;
- Dompé Pharmacovigilance for safety reporting.

The treatment assignment information will be kept confidential and will not be disclosed to any other person than those ones involved in these emergency and safety procedures.

Access to individual patient treatment information will be allowed only in the event of a medical emergency where the knowledge of patient treatment is required to provide the patient with appropriate care.

Any code break and the reason behind it will be recorded (when it was opened, by whom and why) in the relevant section of the eCRF. Code break will be immediately communicated to Dompé, as appropriate.

If the treatment code needs to be broken in the interest of patient safety for a medical emergency, the Investigator is allowed to break the treatment code for the specific patient, even before informing the Sponsor. The Investigator must always notify the Sponsor, so that the reason for any premature unmasking can be documented, by means of a communication to CRO and to Dompé Medical Expert.

The Investigator will inform the Dompé representative (Dompé Medical Expert) if an emergency unmasking was performed without revealing the treatment identity, but only referring to the kit number involved in the unmasking in order to avoid a dissemination of unmasked information.

Dompé Pharmacovigilance, Safety and Surveillance Department will unmask a patient treatment only for reported SAE potentially meeting criteria of a SUSAR, in order to fulfill expedited regulatory reporting requirements. The identity of the treatment will remain unknown to the patient, Investigator, site staff, CRO and Dompé's Development personnel until the study is unmasked. Unblinding events will be recorded and reported in the clinical study report.

9. STATISTICAL CONSIDERATIONS

This study is designed to be a randomized, placebo-controlled, double-blinded, 2-parallel arm, phase II trial in which subjects are randomized (1:1) to ladarixin or placebo.

9.1. SAMPLE SIZE

Sample size calculation was based on results obtained in the phase 2 trial with ladarixin in T1D onset. Considering the following assumptions:

- randomization ratio 1:1 (ladarixin: placebo),
- one-side type I error of 0.05,
- expected difference in favor of ladarixin in terms of responders: ~22.5%, and
- power of 80% to detect the expected treatment effect

a total of 76 evaluable patients are required; to account for a possible 10% of patients not evaluable for the primary variable after enrollment, up to 86 patients will be enrolled.

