Primary Efficacy Endpoint	The proportion of responders at week 27/28 (visit 4), with responders defined as "patients with an HbA1c reduction from baseline of $\geq 0.50\%$ (absolute difference) without episodes of severe hypoglycemia (level 3)
Secondary Efficacy Endpoints	- The proportion of responders at week 11/12 (visit 3)

	
 - The mean difference from baseline in HbA1c assessed at week 11/12 (visit 3) and 27/28 (visit 4) - Average (previous 3 days) daily insulin requirements (IU/kg/day) assessed at week 11/12 (visit 3) and 27/28 (visit 4) - Glycemic Variability by CGM (previous 7 days): time in range (TIR), time above range (TAR) time below range (TBR), standard deviation and coefficient of variation assessed at week 11/12 (visit 3) and 27/28 (visit 4)
Exploratory Endpoints	
 - CCI [REDACTED] - [REDACTED] CCI - CCI [REDACTED] - [REDACTED] - [REDACTED]
Safety Measures	
 - Vital signs (blood pressure and heart rate) & Safety laboratory tests (hematology, clinical chemistry) assessed at screening, week 11/12 (visit 3) and 27/28 (visit 4) - Incidence of Treatment Emergent Adverse Events (TEAEs) recorded from the beginning of study treatment to up to the end of study participation
Statistical Methods	
This study is designed to be a randomized, placebo-controlled, double-blinded, 2-parallel arm experiment in which subjects are randomized (1:1) to ladarixin or placebo. Sample size calculation was based on results obtained in the phase 2 trial with ladarixin in T1D onset. Considering the following assumptions:
 
 • randomization ratio 1:1 (ladarixin: placebo), • one-side type I error of 0.05, • expected difference in favor of ladarixin in terms of responders: ~22.5%, and • power of 80% to detect the expected treatment effect 
a total of 76 evaluable patients are required; to account for a possible 10% of patients not evaluable for the primary variable after enrollment, up to 86 patients will be enrolled.

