the AUC of C-peptide measured during an MMTT performed on week 13 from randomization. Follow-up was extended up to one year. Out of 85 patients enrolled (consent signed), 76 were randomized, 50 to received ladarixin and 26 allocated to placebo; 48 patients in the ladarixin group and 25 in the placebo completed the trial (week 52 observation). The primary and secondary analyses were performed on the ITT population. The primary efficacy analysis of log (AUC [0-2 hrs]+1) of C-peptide response to MMTT showed no statistically significant difference ($p=0.3303$) between the ladarixin and placebo group at Week 13. Overall, there were no clinically relevant treatment effect differences between the treatment groups for other secondary endpoints, such as C-peptide at other time-points, insulin requirement, glucose levels and glucagon levels during the study. On the other hand, the proportion of patients with HbA1c <7% and absence of episodes of severe hypoglycemia was significantly higher at Week 26 ($p=0.0248$) in patients receiving ladarixin as compared with placebo (whole ITT population).

A phase 3 multicenter, double-blind, placebo-controlled study with ladarixin is currently recruiting (ClinicalTrials.gov Id: NCT04628481) and aims to assess the efficacy of ladarixin in patients with new-onset T1D.

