In spite of breakthroughs in the design and action of modern insulin and insulin pharmacotherapy³²⁻⁴⁴, most people with T1D cannot achieve recommended HbA1c targets⁴⁵⁻⁵⁶. This is associated with significant risk for, and high incidence rates of long-term T1D complications (cardiovascular, neural, renal, and ophthalmic) resulting in earlier mortality, no matter how well insulin maintains their glucose control. ***This highlights the need for insulin adjunctive approaches to address the underlying metabolic imbalances beyond dysglycemia. One of the under-appreciated, but emerging complication in many T1D patients is IR***^{14,16-23}. It is associated with negative clinical outcomes^{14,15,17-20,22,23,51-53,55-69} and there are few if any interventions targeting IR^{15,57-59,61,65,66,68,69}, despite an urgent clinical need^{34,40,43,54,70-78}. The most common cause of death in adults with T1D is cardiovascular disease which correlates better with IR than with impaired glucose control disease^{14,16-23}. Although IR is mainly observed in overweight and obese T1D patients^{14,15,17,20,58,79,80}, recent evidence indicates that even lean patients can exhibit IR^{14,15,17,20,59-61,63,65,69,81,82}.

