5.6. INSULIN TITRATION

Patients will self-monitor blood glucose levels, as per their standard practice with self-owned (if applicable) CGM, and will take insulin as prescribed by the PI or their Primary Care Physician (PCP) and/or endocrinologist throughout the study participation.

To ensure standardized glycemic control in the treatment groups, the PI/Study Physician, together with the patient's PCP/endocrinologist will provide guidance for insulin regimen adjustment, with insulin titrated up or down to target HbA1c levels of less than 7% based on the following self-monitored glucose level:

- pre-prandial blood glucose of 70-130 mg/dL

In order to optimize insulin titration, telephone calls (outside scheduled visits) will be scheduled on a regular basis (at least every 30-45 days) to ensure timely evaluation of glucose levels and adjustment of insulin regimen.

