Patients must ensure the CGM sensor is correctly inserted and glucose monitored for at least the 7 days prior to the next visit. Potential study subjects must meet all inclusion and exclusion criteria prior to randomization.

The study subjects will be asked to continue regular glucose monitoring through the recording system as described in Section 5.6 to adjust their insulin intake according to T1D standard of care.

After the screening visit, the sub-investigator/trial coordinator will reach out the subject in at least one occasion to ensure compliance with daily blood glucose measurement as described in Section 5.6 and familiarize with establishing and maintaining contact with the trial staff to report/discuss any possible AEs and/or other aspects of the trial protocol.

Potential study subjects must meet all inclusion and exclusion criteria prior to randomization.

Visit 2: Randomization and start of IMP (Day 1): Within 2 weeks from the screening, the study subject will come to the site in the morning for visit 2. After at least 7 days of CGM data have been downloaded for measurement of glycemic variability outcomes and all inclusion/exclusion criteria have been finally confirmed, eligible patients (enrolled patients) will be assigned a unique sequential randomization number and randomized 1:1 into either ladarixin or placebo, according to the randomization list. Dropouts after randomization will not be replaced. Vital signs will be measured, average (previous 3 days) daily insulin requirements (IU/kg/day) will be recorded, body weight, height, waist and waist/hip circumference will be assessed [REDACTED] and BMI calculated. Blood will be collected for the exploratory outcome measures CCI [REDACTED] and for HbA1c assessment (up to 2 mL).

At the end of the visit, Patient Kits for cycle 1 to 3 will be dispensed; it is the responsibility of the study physician to explain, and make sure that, patient fully understands any appropriate treatment related information. This includes, but is not limited to, treatment schedule, time of administration, time interval from meals, and recording of treatment administration in the Patient Diary.

IMP administration: The patients will begin administering the IMP, while on-site under medical supervision, ideally no later than 11:30 (1st dose of cycle 1). Treatment will proceed at home for the 1st and for additional 6 cycles of 14 days on/14 days off, for a total of 26 weeks.

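### Can 76 evaluable patients and 80% power be accepted when the sample size section gives no placebo responder rate?

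*Protocol*

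**What the plan says.** Section 9.1 and the Statistical Methods row of the synopsis give the same list of planning assumptions: equal allocation, "one-side type I error of 0.05", "expected difference in favor of ladarixin in terms of responders: ~22.5" per cent, and 80% power for that effect. Both conclude that "a total of 76 evaluable patients are required", and both raise enrolment to as many as 86 to allow for 10% not evaluable.

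The stated source is a single sentence: "Sample size calculation was based on results obtained in the phase 2 trial with ladarixin in T1D onset". Section 2.5.2 summarises that trial. Its only responder result is that "the proportion of patients with HbA1c <7% and absence of episodes of severe hypoglycemia was significantly higher at Week 26" with ladarixin (p=0.0248). It gives no proportion for either arm, and its responder definition differs from the one used here, which is an HbA1c fall of at least 0.50 points without level 3 hypoglycaemia (section 7.1).

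Two other statements bear on how often placebo patients might respond. Section 5.6 has "insulin titrated up or down to target HbA1c levels of less than 7" per cent, and this applies to both arms. Section 2.6 says that "most people with T1D cannot achieve recommended HbA1c targets".

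**The concern.** The variance of a difference between two proportions depends on the proportions themselves, so the listed inputs leave the sample size undetermined. A reader who tries to check 76 cannot do so without supplying a placebo rate.

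The choice matters. For a 22.5-point difference, 38 per arm gives 80% power only if the placebo rate is at or below about 10%, or at or above about 67%. Patients enter with a screening HbA1c of at least 7.5%, and insulin in both arms is adjusted towards a value below 7%. Some placebo patients could therefore meet the 0.50-point criterion, and a rate above 10% is not far-fetched.

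The transfer from the earlier trial also looks uncertain. That trial enrolled new-onset patients, while this one requires more than a year of disease and evidence of insulin resistance. At stake is the reading of a negative result: a trial described as having a 20% chance of missing a true 22.5-point effect might have a chance of 30% or more.

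**Working it through.** **Inputs.** From section 9.1: alpha 0.05 one-sided (z = 1.645), power 80% (z = 0.842), difference d = 0.225, 38 evaluable per arm. The placebo rate p is not given, so it is treated as an assumption and varied; the ladarixin rate is q = p + 0.225.

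**Reproducing 76.** The unpooled formula is n per arm = (1.645 + 0.842)² × [p(1−p) + q(1−q)] / d².

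With p = 0.10 and q = 0.325:

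- p(1−p) + q(1−q) = 0.0900 + 0.2194 = 0.3094
- d² = 0.050625
- n = 6.18 × 0.3094 / 0.050625 = 37.8, so 38 per arm and 76 in total.

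The mirror pair, 67.5% and 90%, gives the same answer. The pooled formula at 10% gives a total of 80, so the exact match depends on using the unpooled version.

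**Enrolment.** 76 / 0.9 = 84.4, so 85; the stated 86 is the next even number.

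**Where 38 per arm gives exactly 80%.** Setting n = 38 and solving for p:

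- unpooled: 10.2% or 67.3%
- pooled: 8.7% or 68.8%

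**Across placebo rates.** Unpooled power is Φ(d / √{[p(1−p) + q(1−q)]/38} − 1.645). For example, at p = 0.20 the sum of variances is 0.1600 + 0.2444 = 0.4044, the standard error is √(0.4044/38) = 0.1032, and 0.225/0.1032 − 1.645 = 0.54, giving 70%.

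| Assumed placebo rate | Total N for 80% (unpooled) | Power at 38 per arm: unpooled / pooled / exact score test |
|---|---|---|
| 10% | 76 | 80 / 78 / 80% |
| 15% | 90 | 75 / 73 / 74% |
| 20% | 100 | 70 / 69 / 70% |
| 30% | 114 | 66 / 64 / 64% |
| 40% | 116 | 64 / 63 / 61% |
| 50% | 110 | 66 / 65 / 66% |
| 60% | 94 | 72 / 71 / 72% |

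The minimum is 64 / 63 / 61%, near a placebo rate of 39%. Reading the difference as anything from 22 to 23 points moves the lower solution only to between 8% and 11%.

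**What the table does and does not show.** It is a sensitivity scan. It shows what power would be if the placebo rate were higher; it does not show that the rate is higher. It also uses unadjusted two-proportion tests, whereas section 9.4.2.1 plans a logistic regression adjusted for the stratification factor and baseline characteristics, so every entry approximates the power of the planned analysis.

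**The case for a change.** The strongest case for acting is that this detail is not one left to the statistical analysis plan. The protocol itself fixes the number and states the power, and a reader cannot recover the assumption from anywhere in it. The summary of the earlier trial gives only a p-value, for a different endpoint in a different population. Stating two rates and a source would cost one line.

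The omission stands, and so does the dependence on the placebo rate. A well-written sample size paragraph would give both rates.

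The further step, that the stated 80% should give way to a lower or conditional figure, does not stand. The power is already presented as resting on planning assumptions, one of which is not stated. Section 2.5.2 is a narrative summary, so the absence of proportions there does not mean the sponsor had none. The titration argument shows that some placebo responders are likely, and 10% already allows for some. The figures of 61-64% need a placebo rate near 40%, which nothing in the protocol supports, and section 2.6 leans the other way. Whether new-onset results carry over to established disease is a fair question, but stating the rates would not answer it.

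**Conclusion.** The concern correctly identifies a reporting gap but not an error. The pair 10% and 32.5% returns exactly 76 by a standard formula, so the stated size and power are coherent with one planning value left out. That this pair was the one used is an inference; the protocol does not say so.

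No change follows, because the missing value governs nothing that happens after planning. It does not enter the enrolment target, the randomisation, the primary test or the type I error. The results will report the responder summary by arm (section 9.4.2.1), so a reader of a negative trial will see the placebo rate that occurred and need not rely on the planning value. Writing 61-64% into the protocol would replace one unstated assumption with another that has no support in it.

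If the true placebo rate were 20%, power for a 22.5-point difference would be about 70% instead of 80%, and at 40% about 61-64%. These figures assume 38 informative patients per arm and an unadjusted comparison. A shortfall of that kind is possible but not shown.

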9.3. ANALYSIS POPULATION

The following population will be defined:

- The Safety ([SAF](#)) population will consist of all randomized patients who received at least one dose of the investigational product. Safety population will be analyzed according to the actual treatment received. The SAF population will be used to present results on safety data.
- The Full Analysis Set ([FAS](#)) population will consist of all randomized patients who received at least one dose of the investigational product. FAS population will be analyzed according to the intention-to-treat ([ITT](#)) principle. The FAS population will be used for the primary analysis of the study and to present results on efficacy data.

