9.4.5. Missing data

All reasonable efforts will be made to reduce the rate of missing data. Investigators will be trained about the importance of patient retention and full data capture. Also, any reasonable attempts should be made by the Investigators to emphasize continued patient's participation for the full duration of the trial. However, in order to minimize missing data, if a patient cannot refer to the site for a planned follow-up visit, the Investigator will try to obtain any relevant information from the patients, including documents/laboratory results available from local medical care.

The number of subjects with missing data will be presented under the "Missing" category. Missing values will not be included in the denominator count when computing percentages. When continuous data will be summarized, only the non-missing values will be evaluated for computing summary statistics.

For the primary analysis, since patients who discontinue the IMP will not be withdrawn from the study but will be asked to complete safety and efficacy assessments as per the protocol, missing data due to intercurrent events will be addressed by using multiple imputation based on retrieved dropouts information. Retrieved dropout patients are defined as patients who discontinue study treatment and decide to remain in the study by following the schedule of assessments and continuing to adhere to protocol requirements. If not enough data were retrieved after study treatment discontinuation to assure the convergence of the MI-RD regression model (the final decision will be done at the time of the analysis and reported in the CSR), the same multiple imputation model will be fit using data from subjects of control group, washing-out the effect of treatment. This approach does not assume benefits for ladarixin in case of discontinuation and limits a post-discontinuation clinical effect to that of placebo. Specific sensitivity analyses will be defined in the SAP to assess the robustness of results on primary endpoint versus assumptions used in the statistical model for the main estimator.

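### Does padding 76 to 86 for non-evaluable patients leave the primary full-analysis-set test short of its stated 80% power?

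*Protocol*

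**What the plan says.** Section 9.1 and the synopsis rest on a one-sided type I error of 0.05, 1:1 allocation, a responder difference of about 22.5 points and 80% power, which gives 76 evaluable patients. The padding follows: "to account for a possible 10% of patients not evaluable for the primary variable after enrollment, up to 86 patients will be enrolled". The figures are said to come from the phase 2 trial of ladarixin in new-onset type 1 diabetes.

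Section 9.3 defines the full analysis set (FAS) as all randomized patients with at least one dose, analysed by allocation, and adds: "The FAS population will be used for the primary analysis of the study and to present results on efficacy data". Section 6.1.2 puts enrollment, randomization and the first dose at Visit 2: "eligible patients (enrolled patients) will be assigned a unique sequential randomization number and randomized 1:1", and "The patients will begin administering the IMP, while on-site under medical supervision".

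Section 9.4.5 says that "missing data due to intercurrent events will be addressed by using multiple imputation based on retrieved dropouts information". If too few such patients are available for the model to converge, the same model is fitted to control-arm data. Of that fallback it says: "This approach does not assume benefits for ladarixin in case of discontinuation and limits a post-discontinuation clinical effect to that of placebo".

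On the source trial, section 2.5.2 says: "The primary and secondary analyses were performed on the ITT population".

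**The concern.** Dividing by 0.9 is the right correction when the lost patients leave the analysis and those who remain carry the full effect. Here the analysis set keeps anyone who took a dose. The first dose is supervised at the randomization visit, so few patients lost after enrollment would fall outside the FAS. If their outcomes are filled in at the placebo rate, they count in the denominator but add nothing to the difference.

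On that reading the stated 80% describes 76 complete cases, while the test that decides the trial sees a smaller difference in 86 patients. Section 9.1 does not say whether 22.5 points is a complete-case or an FAS difference, so a reader cannot tell which was powered. At stake is whether the trial is quietly underpowered at its own 10% allowance.

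**Working it through.** **Inputs.** One-sided alpha 0.05 (z = 1.645), power 80% (z = 0.842), difference d = 0.225, 38 per arm evaluable, 43 per arm enrolled, 10% allowance (all from 9.1). The placebo rate pC is not given. It is an assumption here, back-solved from 76.

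**Reproducing 76.** With the unpooled z-test, n per arm = [pT(1−pT) + pC(1−pC)] × (1.645 + 0.842)² / d². At pC = 0.10 and pT = 0.325 this is 0.3094 × 6.183 / 0.0506 = 37.8, so 38 per arm and 76 in all. By symmetry 67.5% versus 90% gives the same. With pooled variance under the null, 8.5% versus 31% and 69% versus 91.5% give 37.65, again 76. Power at 38 per arm is 80.2% (unpooled) or 80.3% (pooled).

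**Reproducing 86.** 76 / 0.9 = 84.4, so 85, and 86 is the next even number. In reverse, 86 × 0.9 = 77.4, which is at least 76. The division is correct.

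**Power of an FAS test at 86.** Let s be the share of randomized patients imputed at the placebo rate. The placebo arm is unchanged, and the expected difference becomes d × (1 − s). For s = 0.10 it is 0.9 × 22.5 = 20.25 points. At pC = 0.10 the ladarixin rate is 0.3025, the standard error is √[(0.3025 × 0.6975 + 0.10 × 0.90) / 43] = 0.0837, and power is Φ(0.2025 / 0.0837 − 1.645) = Φ(0.776) = 78.1%. The other cases follow in the same way:

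| Scenario at 43 per arm | 10% (unpooled) | 67.5% (unpooled) | 8.5% (pooled) | 69% (pooled) |
|---|---|---|---|---|
| 22.5 points is the FAS effect | 84.3% | 84.3% | 84.5% | 84.5% |
| s = 3/76 = 3.9% | 82.0% | 80.9% | 82.4% | 81.2% |
| s = 5% (half of the 10%) | 81.4% | 80.0% | 81.8% | 80.2% |
| s = 10% (all) | 78.1% | 75.1% | 78.6% | 75.4% |

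The 3/76 row uses section 2.5.2: 76 randomized, 48 + 25 = 73 completed week 52, so 3 did not. Power falls to 80% when s is between 4.9% and 7.9%, which is about 4 to 7 of 86 patients.

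**A mixed case.** Suppose 22.5 points is an ITT effect that the source trial's 3 of 76 had already diluted. The undiluted effect is then 22.5 / (1 − 3/76) = 23.4 points. Diluting it again by the full 10% gives 0.9 × 23.4 = 21.1 points and power of 79% to 81%.

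**Limits of these figures.** They treat imputed values as observed. A simulation with draws from control and Rubin pooling gave 77.7% (placebo rate 10%) and 74.2% (67.5%) for s = 10%. A rougher one on the log odds ratio gave about 77% and 70%. The four rate pairs are not the only ones that return 76: a continuity-corrected formula gives placebo rates near 3% and 74.5%, where full dilution at 86 leaves 80.4% and 75.4%.

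**The case for a change.** The strongest case for acting is that this is not detail left to the SAP. The sample size, the analysis set and the imputation rule are all fixed in the protocol, and they do not describe the same patients. The fallback is a realistic prospect too: 10% of 86 is about 9 patients over both arms, and retrieved dropouts may be too few to fit a model. The remedy would be only wording. These points stand as far as they go, and the conditional figure of 75% to 79% is sound arithmetic.

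What does not stand is the step from there to a design that misses 80%. Three conditions must hold together, and the documents fix none of them.

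- **Complete-case effect.** The source trial's analyses used its ITT population, and section 2.5.2 reports no complete-case responder result. The word evaluable in 9.1 points the other way, so the question is open.
- **All 10% dosed and missing.** The source trial lost 3.9% over 52 weeks, a longer period than this trial's 28. Sections 5.3.2 and 6.3.1 keep patients who stop treatment under efficacy observation, and 9.4.5 adds retrieval of local laboratory results.
- **All imputed at the placebo rate.** Control-based imputation is the second choice. The imputation also covers only data missing because of intercurrent events. Patients missing for other reasons, or never dosed, may be the ones 9.1 calls not evaluable, and for them the 1/0.9 padding is coherent.

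**Conclusion.** The plan does not contradict itself here and no power error is shown. The padding is correctly computed, and power at 86 lies between about 75% and about 84%, depending on facts that 9.1 leaves unstated. The intermediate cases, half of the 10% diluted or the source trial's non-completion, sit at 80% to 82%. Only full dilution of a complete-case effect is clearly below. At the low placebo-rate solutions even that costs under 2 points; the loss of about 5 points needs a placebo responder rate near 68% or higher, which no document supports. For scale, reading the approximate 22.5 as 22 points moves power at 38 per arm to between 78.2% and 79.0%, a change of similar size to the smaller losses.

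The true remainder is a reporting gap: the assumed responder rates, the test and the population behind the 22.5 points. Writing these down would help a reader judge a null result, but it would not alter the enrollment of 86, the primary analysis or any conclusion. A larger sample cannot be justified either: full dilution would call for 90 to 100 patients, and no figure in that range can be chosen without the placebo rate. All of this rests on back-solved rates and normal-approximation tests.
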